B	SCR up to 90 days	RND	Symptomatic nonhormonal medical treatment as determined by the investigators and/or watch and wait														12 wk FUP	

Groups A1, A2, and A3 treated daily with vilaprisan 2 mg during treatment periods
 Group A1: 4/8 treatment periods of 12 weeks, each separated by 1 bleeding episode (3/1 regimen)
 Group A2: 2/4 treatment periods of 24 weeks, separated by 2 bleeding episodes (6/2 regimen)
 Group A3: 3/6 treatment periods of 12 weeks, each separated by 2 bleeding episodes (3/2 regimen)
 Group B treated with standard of care (SoC) symptomatic nonhormonal medical treatment as determined by the investigators and/or watch and wait.
 B = bleeding episode; FUP = follow-up; RND = randomization; SCR = screening; trt = treatment; wk = week.

The **primary safety variable** is the percentage change in bone mineral density (BMD) of lumbar spine from baseline to about one year after start of treatment (SoT) (please refer to section 6.5.1 for details). With the implementation of Protocol Amendment 10 (version 7.0), the study is being prepared for closure. A thorough safety monitoring is performed in subjects before this closure, including a recovery BMD scan. All subjects who received vilaprisan treatment will be asked to undergo a BMD scan at least 6 months after the last intake of vilaprisan, to document absence of

bone loss or adequate recovery after the end of treatment. Subjects randomized to treatment group B who are still in the study with implementation of Protocol Amendment 10 (version 7.0) should also undergo a BMD scan at the safety closeout visit, unless they had a BMD scan performed within the last 3 months prior to the safety closeout visit.

4. General Statistical Considerations

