	2 nd	Diary	Last visit before the safety closeout visit
	3 rd	Max (SV last visit end date, “last visit” from eCRF)	SV last visit end date
	4 th	If no study drug exposure (FAS not SAF) use SV last visit end date	
		Reference end date will finally be replaced by maximum of reference start date and reference end date.	
TP start date	1 st	eCRF (TP1: reference start date) Exception 6/2 regimen: split protocol planned TPs with 168 days, assign start and end dates of these with CRF collected for planned TPs and derived start and end dates of split TPs.	TP1: reference start date TPs will be defined as consecutive 84-day time intervals starting with the date of randomization.
TP end date (excluding last TP)	1 st	eCRF exception 6/2 as above	
TP end date (last TP)	1 st	Reference end date	

eCRF = electronic case report form; EoT = end of treatment; SV=subject visit; TP = treatment period; VPR = vilaprisan

Treatment period

For subjects in treatment groups A1, A2, and A3, each treatment period (TP) consists of three subsequent 28-day periods. In case of premature discontinuation of study drug the last 28-day period of the respective treatment period might be shorter than 28 days. If a subject took the study drug for more than 84 days of a treatment period, the respective treatment period will be longer than 84 days, in contrast. Subjects treated in 3/1 and 3/2 regimens, have the first break after TP 1. Subjects treated in 6/2 regimens have two planned TPs before the first break.

The definition of TP here described which will be used in the analysis, differs from the definition of TP used in the protocol and Section 3 to describe the 6/2 treatment regimen. The definition used in the analysis allows for a better comparison between treatment regimens and is consistent with the reporting of other studies of the VPR project.

The first TP starts with the reference start date, the last TP ends with the reference end date. Start and end of a TP will be identified based on eCRF entries (EXCATN=1).

In 6/2 regimen, the protocol plans for TPs with 168 days each. The CRF only collects start and end dates of these protocol planned TPs.

For the analysis, the planned protocol TPs are split into 2 Analysis TPs:

- The first Analysis TP is assigned first available odd TP number and ends with day 84 (or the maximum number of available days if less than 84 days are reported).

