- The second Analysis TP is assigned the next higher even TP number, starts with day 85 and ends with the last day reported in the original protocol TP, even if this exceeds a total of 168 days.

For example, protocol TP1 = analysis TP1 + analysis TP2. Protocol TP2 = analysis TP 3 + analysis TP 4 etc.

If the original planned protocol TP is less than 85 days, no such second evenly numbered Analysis TP will be assigned. As a result of this a subject in 6/2 regimen might have Analysis TP 1, TP 3 and TP 4, but no Analysis TP 2.

If the end date of the current treatment period is equal to the start date of the next treatment period based on CRF entries, it is assumed that the current treatment period ended one day earlier. The end date of the current treatment period is therefore moved back by one day.

For all TPs excluding the last TP, in case end of TP date is still missing, it will be replaced by the date of the last study drug intake within the respective TP according to diary (EXCATN=5 and EXMEDN>=1).

Subjects in treatment group B don't have any breaks. In the treatment group B TPs will be defined as consecutive 84-day time intervals starting with the date of randomization.

Replacement rules for missing end date of the last TP are analogue to those described for reference end dates.

TPs will be numbered sequentially.

Time intervals

Due to the complex visit schedule of the studies, a time-interval based approach is chosen to present data over time. Therefore, time intervals are defined which are used for different analysis topics.

The selection of time intervals used for a certain analysis topic will be described within each section.

An overview of the time intervals is given in [Figure 4-1](#).

Figure 4-1: Time interval overview

BL/Post baseline	Post baseline																										
Intervals A	Treatment Phase																		FUP Phase								
Intervals B	TP1 + BR1						TP2 + BR2						TPx						FUP1+2			FUP ...					
Intervals C	TP1			BR1			TP2			BR2			TPx			FUP1			FUP2			FUP ...					
Intervals D	BL	BL	BL	TP1	TP1	TP1	BR1	BR1	BR1	TP2	TP2	TP2	BR2	BR2	BR2	TPx	TPx	TPx	FUP	FUP	FUP	FUP	FUP	FUP	FUP	FUP	FUP
	1-28	29-56	57-x	1-28	29-56	57-84	1-28	29-56	...	1-28	29-56	57-84	1-28	29-56	...	1-28	29-56	57-84	1-28	29-56	57-84
AE Intervals	Pre-treatment			"on" (TP1 + 8d)			"off"			"on" (TP2 + 8d)			"off"			"on": TPx + 8d			"off"			Post-treatment (Start: day 61 after EoT)					

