Exit examination	BL, last value within interval																		Exit examination (Start: EoT -7 days); last value within this interval								

Abbreviations: BL: Baseline, TP: Treatment Period, BR: Break (not applicable for Treatment group B), FUP: Follow-up, d: days, m: months.

Treatment periods and breaks will be identified as described above. Baseline/Pre-treatment phase starts with the date of informed consent and ends on the day before the start of the Treatment phase.

The Treatment phase starts and ends with the reference start and end date. The FUP phase starts on the day after the end of the treatment phase and ends on the maximum of the last date at which a visit took place (visit end date), and the “last visit” as collected on the eCRF page. For patients who did not complete the planned schedule of TPs, a break period will be defined after the end of the last TP, as described in the previous subsection ‘Break period’. This break period will be followed by the FUP.

Baseline, Treatment phase, FUP phase, TPs and breaks are subdivided into subsequent periods of different lengths (28, 84, or 168 days). Exit examination time intervals include the baseline measurement, i.e. the last non-missing value before reference start date, and the exit examination which is defined as the last non-missing value at or after the reference end date – 7 days, which is per definition the safety closeout visit for subjects who perform this visit.

For treatment group B, consecutive TPs (84-day time intervals) in the treatment phase will be used for intervals B and intervals C. Each TP will be subdivided into subsequent consecutive 28-day periods for intervals D. For intervals for assessing AEs in the treatment phase, consecutive TPs will be ended at day 60 after the reference end date. For the assessment in the follow-up phase, same rules will be used as VPR treatment groups.

Details on time intervals for AE presentation are given in Section 6.5.3.5.

Details on time intervals for BMD presentation are given in Section 6.5.1.

Break period

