6.2.3.3 Ultrasound examination related variables

- Percent change in volume of largest fibroid compared to baseline (baseline = last value obtained before randomization; measured by ultrasound examination)
- Percent change in volume of 3 largest fibroids compared to baseline (measured by ultrasound)
- Percent change in volume of uterus compared to baseline (measured by ultrasound)
- Percentage of subjects with a volume reduction of $\geq 25\%$ of the 3 largest fibroids (measured by ultrasound)
- Percentage of subjects with a volume reduction of $\geq 25\%$ of the largest fibroids (measured by ultrasound)
- Percentage of subjects with a reduction of $\geq 25\%$ of uterine volume (measured by ultrasound)

Analysis will be done by treatment group and visit/time interval B (according to [Figure 4-1](#)).

If multiple volume assessments by ultrasound are available for a time period, the smallest volume will be used for the baseline time period, and the largest volume will be used for any other time periods of Intervals B.

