6.5.1 Primary safety variable

The primary safety variable is the percentage change in BMD of lumbar spine (using the central reading results) from baseline to about one year after SoT. One year is defined as ‘Month 12 on treatment’ in Table 6-1, i.e. Day 300 after reference start date to Day 420 after reference start date, but no later than the reference end date + 60 days.

The primary safety variable will be analyzed using descriptive statistical methods and two-sided 95% confidence interval (CI) for the mean difference for the percentage change in BMD of lumbar spine from baseline to about one year after SoT will be calculated for each vilaprisan treatment group as compared to treatment group B. Additionally, two-sided 95% CI for each treatment group will be calculated. The primary variable is assumed to be at least approximately normally distributed.

For the percentage change in BMD of lumbar spine from baseline to other time points defined in Table 6-1, the descriptive statistics will also be provided by treatment group.

The percentage change in BMD of lumbar spine from EoT BMD will also be evaluated using summary statistics by treatment group and time interval or month for post treatment period defined in Table 6-1.

The time intervals and month named in Table 6-1 will be presented in tables and figures unless otherwise specified. Month equals 30 days.

Table 6-1: Definition of month and time intervals for BMD summary

	Month	Time interval
Baseline	Baseline	Baseline if no Visit 2-repeat scan exists, Visit 2 scan will be used as baseline. Otherwise, Visit 2 -repeat scan will be used. The BMD baseline visit will be marked in the dataset transferred from ICON’s Medical Imaging group. (refer to section 4.5)
On treatment period : From reference start date to reference end date + 60 days	Month 1	N/A
	Month 2	If a BMD value performed after the reference start date has been marked as baseline value, it will be analyzed as baseline value and will be excluded from the analysis for on treatment period.
	Month 3	
	Month 4	
	Month 5	Month 6 on treatment Day 120 after reference start date to Day 240 after the reference start date, but no later than the reference end date + 60 days
	Month 6	
	Month 7	
	Month 8	
	Month 9	N/A
	Month 10	Month 12 on treatment Day 300 after reference start date to Day 420 after reference start date, but no later than the reference end date + 60 days
	Month 11	
	Month 12	
	Month 13	
	Month 14	

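### Rows with the same TP number set vilaprisan beside group B at different times since start (0 to about 4 months apart if a bleeding episode takes 28 days), and Interval B rows also differ in length

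*SAP*

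**What the plan says.** For group B, Section 4.5 (Treatment period) says "Subjects in treatment group B don't have any breaks", and "In the treatment group B TPs will be defined as consecutive 84-day time intervals starting with the date of randomization". Under Time intervals it adds: "For treatment group B, consecutive TPs (84-day time intervals) in the treatment phase will be used for intervals B and intervals C". These blocks are cut into 28-day periods for Intervals D.

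For vilaprisan, TP dates come from the dosing entries in the eCRF, and each break runs until the day before dosing restarts. Section 3 describes the regimens: "Group A1: 4/8 treatment periods of 12 weeks, each separated by 1 bleeding episode (3/1 regimen") and "Group A2: 2/4 treatment periods of 24 weeks, separated by 2 bleeding episodes (6/2 regimen"). A3 has 12-week periods separated by two bleeding episodes. For analysis, A2's 24-week periods are split in two, and "Subjects treated in 6/2 regimens have two planned TPs before the first break".

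Section 4.1 has the outputs show A1, A2, A3 and B. For fibroid and uterine volume, Section 6.2.3.3 says: "Analysis will be done by treatment group and visit/time interval B". Hemoglobin, hematocrit, ferritin and endometrial thickness use Intervals C. UFS-QoL and UF-DSD use Intervals D.

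BMD is handled differently. Its one-year window in Section 6.5.1 is counted from the reference start: "Day 300 after reference start date to Day 420 after reference start date, but no later than the reference end date + 60 days".

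**The concern.** In a vilaprisan arm, a TP number says how many courses have been given. In group B, which has no courses, it says only how much time has passed. Printing both under one label invites the reader to compare along the row, yet the two entries refer to different times since start.

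The secondary objective is efficacy in comparison with standard of care, and most longitudinal displays that serve it are built on these rows. They are descriptive, so no model adjusts for elapsed time. Anything that drifts over time in group B is read earlier there than in vilaprisan. The SAP justifies its analysis TPs as easing comparison between regimens. That reason fits A1 against A2 against A3, but it does not carry over to a group without dosing cycles.

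The row lengths also differ. An Interval B row normally covers a TP plus its break in vilaprisan but only 84 days in group B. Section 6.2.3.3 takes the largest post-baseline volume in each interval, so a longer window gives more opportunity for a high value.

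**Working it through.** The SAP states no offset, so there is no figure to reproduce. What follows is date arithmetic.

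**Inputs.** TP length is 84 days and group B has no breaks (Section 4.5). The regimens are as in Section 3. Day 1 is the reference start date: first intake for vilaprisan, randomization for group B. Let b1 be the length of a one-bleed break and b2 that of a two-bleed break. Neither is given in days. Assumption: 28 days per episode, so b1 = 28 and b2 = 56.

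**Check on the assumption.** Planned course lengths become:
- A1: 4×84 + 3×28 = 420 days
- A2: 4×84 + 56 = 392 days
- A3: 3×84 + 2×56 = 364 days

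All three fit the plan's description of about one year and the Day 300–420 window.

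**Start of TPk.**
- B: 84(k−1) + 1
- A1: (84 + b1)(k−1) + 1, lag (k−1)·b1
- A2: lag b2 × the whole part of (k−1)/2
- A3: (84 + b2)(k−1) + 1, lag (k−1)·b2

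Start day, with the lag behind B in days:

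| Row | B | A1 | A2 | A3 |
|---|---|---|---|---|
| TP2 | 85 | 113 (28) | 85 (0) | 141 (56) |
| TP3 | 169 | 225 (56) | 225 (56) | 281 (112) |
| TP4 | 253 | 337 (84) | 309 (56) | not in the one-year schedule |

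The largest lag is 112/30 = 3.7 months, using the SAP's 30-day month.

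**Range for 21 to 42 days per episode.**
- A1: 21–42 days at TP2, 42–84 at TP3, 63–126 at TP4
- A2: 0 at TP2, 42–84 at TP3 and TP4
- A3: 42–84 at TP2, 84–168 at TP3

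**When same-numbered rows share no day.**
- A3 TP3 starts on day 169 + 2·b2 and B TP3 ends on day 252. There is no overlap if 169 + 2·b2 ≥ 253, that is b2 ≥ 42.
- A1 TP4 starts on day 253 + 3·b1 and B TP4 ends on day 336. There is no overlap if 253 + 3·b1 ≥ 337, that is b1 ≥ 28. At b1 = 21, A1 TP4 starts on day 316 and the rows share 336 − 316 + 1 = 21 days.
- At b1 = 28, A1 TP4 covers days 337–420. That is exactly B TP5, a row that a four-period A1 course does not have.

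**Length of an Interval B row at 28 days per episode.**
- B: 84 days
- A1: 84 + 28 = 112 days
- A3 and even-numbered A2 TPs: 84 + 56 = 140 days
- Odd-numbered A2 TPs: 84 days

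Figure 4-1 shows the last planned TP without a break.

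**The case against.** The strongest counterargument is that the comparisons that matter most do not use these rows, and this stands. The planned confidence intervals for differences from group B concern BMD, in windows from the reference start. The only secondary efficacy variable, number of bleeding days, is counted over the whole evaluation period and normalized to 28 and 365 days. The TP displays concern other efficacy variables or descriptive safety, with no by-TP contrast against B specified. Endometrial thickness is also shown by Intervals A and at the exit examination, neither of which depends on TP number.

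It is also fair that calendar windows are no clean substitute. Intervals C and D separate treatment from break for endpoints that may differ between the two. The Table 6-1 windows would mix these states, leave days 1–119 and 241–299 uncovered, and lose the 28-day detail. That argues against replacing TP rows, but not against adding calendar rows.

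A reader might infer that every row from TP2 on is off by two to five months. The SAP does not support this. A2 TP2 is aligned by definition, and A1 TP2 is about one month off under the base assumption. Five months (150 days) at A3 TP3 needs two-bleed breaks of 150/2 = 75 days. A3 TP4 would start on day 421 at 56-day breaks, in the second year that no Subgroup 2 subject reached. Nor do A1 TP4 and B TP4 fail to overlap at every break length, as the 21-day case shows.

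**Conclusion.** The misalignment follows directly from the TP definitions in Section 4.5, and no rule in the SAP realigns group B for these displays. At 28 days per bleeding episode the lag runs from 0 (A2 TP2) to 112 days (A3 TP3), or 0 to about 4 months. The size rests entirely on that assumed break length, but the direction does not: from TP3 on, every vilaprisan arm is read later than group B. Interval B rows are unequal as well, which matters for the largest-volume rule.

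A reader might go further and put a figure on the fibroid growth hidden in group B, or say that the difference from vilaprisan is understated. The SAP gives no growth rate, and the unequal windows act on the same endpoint, so neither the size nor the net direction of an effect on the volume comparison can be stated. The primary BMD result and the normalized number of bleeding days are untouched. This is a worthwhile repair to descriptive tables that serve the secondary objective, and it does not threaten the main conclusions.

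**What to change.** 1. Keep the TP rows for comparing the vilaprisan regimens with each other.
2. For fibroid and uterine volume, add rows by time since reference start for vilaprisan against group B, for example the Day 120–240 and Day 300–420 windows already in Table 6-1. Apply the same rule for multiple values to all arms, so that the largest volume is taken over the same window of days since start.
3. Give the same rows as a supplement for hemoglobin, UFS-QoL and endometrial thickness, leaving the Interval C and D displays in place.
4. Footnote every table by Interval B, C or D that includes group B: its TP rows are time since randomization, and vilaprisan rows with the same number may fall later.

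The cost is SAP wording and a few extra tables from data already collected. The downside is that calendar windows mix on-drug and break values in the vilaprisan arms. Flag this in the tables, for instance with the number of values taken on treatment and in a break.

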4.5 Data Rules

Reference Start/End dates

For vilaprisan (VPR), the reference start and end dates refer to the first and last study drug intake and will be identified based on the eCRF entry (EXCATN=1). For subjects with study drug exposure unknown, the randomization date will be used as the reference start date, and the end date of last scheduled/ unscheduled visit according SV (Subject Visits dataset) will be used as the reference end date.

Missing or partially missing eCRF end dates will be replaced by the date of the last study drug intake according to the diary. In case there is no study drug intake recorded in the diary, the date of the last available visit/contact will be used, which is the maximum of the end date of last scheduled/ unscheduled visit according SV (Subject Visits dataset), and the “last visit” as collected on the eCRF page for Disposition dataset. For subjects randomized to VPR who did not take any treatment (FAS not SAF), the last available visit date will be used as the reference start date and the reference end date.

For treatment group B the reference start date is defined by the randomization date. The reference end date is defined by the start date of the End of Treatment (EoT) visit (unscheduled EoT visits not considered). Missing EoT visit dates will be replaced by the end date of the last available visit before the safety closeout visit (refer to Table 4-1). If a subject in treatment group B has no safety

closeout visit, missing EoT visit dates will be replaced by the date of last scheduled/ unscheduled visit according SV (Subject Visits dataset).

For both VPR and treatment group B, the reference end date after the missing replacement with the rules defined above should be no earlier than the reference start date. Otherwise, the reference end date will finally be replaced by the reference start date.

For any analysis, if date of first study drug exposure/ date of last study drug exposure is used, the reference start/end date for treatment group B defined as above will be used for the analysis in treatment group B, if applicable.

Table 4-1 Replacement rules for missing reference start/end dates and TP start/end dates

	Choice	VPR regimens	Treatment group B
Reference start date	1 st	eCRF	Randomization date
	2 nd	a. If study drug exposure unknown, use randomization date b. If no study drug exposure (FAS not SAF) use SV last visit end date	
Reference end date / Last TP end date	1 st	eCRF	EoT visit start date

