All VPR treatment groups include a treatment-free period following the end of TPs in 3/1 and 3/2 regimens, or end of TPs 2, 4, 6 etc. in 6/2 regimen. The length of the break period will vary depending on whether 1 or 2 bleeding episodes take place. In any case, the break period starts the day following the date of stop date of study drug administration in a particular TP, and ends the day before the study drug administration starts in the next TP.

If a subject did not start the next planned TP, due to the clinical hold or any other reason, there is no end date for the break period. In this case, a theoretical end date will be generated. For this purpose, information on the start of the previous TPs will be used. If a subject started TP1 at the i-th Day of her bleeding episode, the theoretical start date of TP2 will be assumed as the i-th Day of the bleeding episode which would have triggered re-starting medication during the treatment break (first or second bleeding depending on treatment regimen). The theoretical end date of the break period will then be assumed as the day before the theoretical start date of TP2. For TPs beyond TP2 the average of the i-th Days of the menstrual cycles when previous TPs started will be calculated and considered as start of the theoretical absent TP. This definition for theoretical end date for the break period depends on the subject experiencing a bleeding episode following the end of the TP. If no bleeding episode starts (spontaneous or induced), then the break period is considered until the end of subject observation.

This theoretical end date will be used in the analysis of number of bleeding days.

For subjects in the 6/2 regimen the break period will follow the end of TP2 or any TP with an even number. If it is necessary to define a theoretical end of the break period, as described in the previous paragraph, this will only occur if the subject started TP2 or any TP with an even number. But for the calculation of the variable number of bleeding days, if a subject withdrew while receiving treatment,

in order to use all information available at the time of analysis, the theoretical end date for the break period of the incomplete TP will be generated regardless the TP with an even or odd number.

Baseline for general parameters

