In general, the last valid, non-missing value prior to the Reference start date will be considered as baseline value. For variables analyzed by 28-day periods, the baseline period corresponds to the last 28 days before the reference start date. This definition does not apply to analyses related to menstrual blood loss where a specific definition for baseline menstrual blood is defined (see baseline menstrual blood loss for 28 days).

Bleeding caused by conducting endometrial biopsy

If an endometrial biopsy was conducted, bleeding on the day of intervention and the 3 days thereafter will not be considered in the bleeding related evaluation, i.e., bleeding/spotting on the day of biopsy and 3 days thereafter will not be considered as day(s) with bleeding/spotting and MP values will be set to 0 mL. This rule is applicable for all bleeding related efficacy analyses.

A biopsy will be regarded as conducted if the intervention was attempted, either successfully or unsuccessfully. Successful means that the date of biopsy is given and 'Biopsy sample obtained - Not done' is not ticked in the eCRF. Unsuccessful means that the date of biopsy is given, 'Biopsy sample obtained - Not done' is ticked in the eCRF, and the reason 'Unsuccessful attempt' is selected.

Baseline menstrual blood loss for 28 days

Baseline menstrual blood loss for 28 days is defined as the sum of volume of menstrual blood loss data of respective days in the baseline cycle. If baseline cycle length is more than 28 days, only data from the first day of cycle to the 28th day of cycle will be used. If baseline cycle length is less or equal than 28 days, data from the first day of cycle to the last day of cycle will be used.

Baseline menstrual cycle

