6.5.3.6 Laboratory parameters

For immunology and coagulation parameters Intervals ‘BL/Post baseline’ will be used, while for all other laboratory measurements the following time intervals will be considered:

- Intervals C (according to Figure 4-1)

The tabulation will follow in principle the Bayer Global Standard Tables catalogue (currently V 4.0 default), with the necessary modifications like for time interval presentation instead of visit presentation.

The maximum or minimum measurement within the time interval will be used for calculations, following a worst-case approach (for details please refer to Appendix 2). Scheduled as well as unscheduled measurements will be considered.

Central as well as local lab measurements are available. Summary statistics will be provided based on central lab. Local lab measurements will be listed.

Values below the lower limit of quantification (LLOQ) will be set to LLOQ/2.

Values above the upper limit of quantification (ULOQ) will be set to ULOQ.

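### In group B a reading taken on the randomization date counts as on-treatment, while the same reading is pre-treatment in a vilaprisan subject who starts dosing later (SAP 4.5)

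*SAP*

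**What the plan says.** All the date rules are in SAP Section 4.5.

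- **Baseline value:** "In general, the last valid, non-missing value prior to the Reference start date will be considered as baseline value". The exit-examination definition under Time intervals uses the same strict cut-off.
- **Baseline phase:** "Baseline/Pre-treatment phase starts with the date of informed consent and ends on the day before the start of the Treatment phase".
- **Treatment phase:** "The Treatment phase starts and ends with the reference start and end date".
- **Group B:** "For treatment group B the reference start date is defined by the randomization date", and "In the treatment group B TPs will be defined as consecutive 84-day time intervals starting with the date of randomization". Table 4-1 agrees.
- **Vilaprisan groups:** "For vilaprisan (VPR), the reference start and end dates refer to the first and last study drug intake".

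No rule covers visit-based values obtained on the reference start date itself. Section 6.1.2 refers back to 4.5, but describes baseline as the reading nearest to study drug administration. Section 6.2.3.3 sets the baseline for the largest fibroid's volume as the last value before randomization, in every group.

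**The concern.** The boundary between baseline and TP1 is tied to a different event in each arm: randomization in group B, the first tablet in A1 to A3. With a strict cut-off, a reading made on the randomization date can change status by arm alone. In group B it cannot be baseline and becomes the first day of TP1. In a vilaprisan subject dosed later it is pre-treatment and may be her baseline.

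Two things are at stake. First, group B's baseline moves back to an earlier screening reading. Second, where the SAP keeps the most adverse value in an interval, or counts a finding seen at least once, a reading that reflects no allocated management can enter group B's TP1 result. The comparator's TP1 then has an extra chance to record an extreme value that a later-dosed vilaprisan subject does not have.

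**Working it through.** The plan gives no figure to reproduce, so this is a check of the date rules. Let R be the randomization date and R + k the day of the first tablet. The SAP gives no value for k. Take a visit-based value obtained on day R.

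| | Group B | Vilaprisan, k = 0 | Vilaprisan, k ≥ 1 |
|---|---|---|---|
| Reference start date | R | R | R + k |
| Last day of baseline phase | R − 1 | R − 1 | R + k − 1 |
| Day-R value eligible as baseline | No | No | Yes |
| Interval holding the day-R value | TP1, day 1 | TP1, day 1 | Baseline |

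Group B differs from every vilaprisan subject with k ≥ 1. With k = 0 the arms are treated alike, although a same-day pre-dose value is lost from baseline there too.

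**Does k ≥ 1 occur?** Yes, in some subjects. The FAS definition in Section 5.1 excludes vilaprisan subjects who were randomized but had not started TP1 when the study was paused, so randomization and first dose were not always on the same day. The Break period rule also describes TP1 by its position in a bleeding episode ("If a subject started TP1 at the i-th Day of her bleeding episode"). That sentence serves to derive theoretical break end dates, so it is indirect evidence. Neither place gives the frequency or length of the gap.

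**Where a day-R value can enter a worst-value or any-occurrence result in group B's TP1:**

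- Laboratory values (6.5.3.6, Intervals C): "The maximum or minimum measurement within the time interval will be used for calculations, following a worst-case approach". Appendix 2 takes the lowest value for hemoglobin, ferritin and estradiol. The hemoglobin threshold tables (6.2.3.6.2 and 6.2.3.6.3) also use Intervals C.
- Estradiol (6.5.3.7): lowest value per interval, and counts below 13 and 30 pg/mL at any visit in the interval.
- UFS-QoL (6.2.3.5.2): worst score within Intervals D, which are 28-day periods. If no other questionnaire fell in days 1 to 28, the day-R score would be the whole result for that period.
- Fibroid and uterine volumes (6.2.3.3): smallest volume in the baseline period, largest in any later Interval B.
- Ovarian cysts above 3 cm (6.5.3.4): counted if seen at least once in the interval.

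**Where this route does not reach:**

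- Primary BMD (4.5 and 6.5.1): baseline is the Visit 2 scan or its repeat, and the one-year window opens at Day 300.
- Menstrual blood loss (4.5): it has its own baseline-cycle definition.
- Number of bleeding days (4.5 and 6.2.2): counted over an evaluation period, with no baseline value.
- Vital signs (6.5.3.9): summarized by visit, with no worst-value rule.
- CGI-I (6.2.3.5.3): a frequency table by visit.

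**Internal consistency.** For group B, Section 4.5 substitutes the reference start date wherever first drug exposure is used. Read that way, the nearest-reading wording of 6.1.2 would select the day-R value as group B's baseline, while the strict rule of 4.5 excludes it. Both cannot be programmed.

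**The case against.** The strongest reply is that the SAP does not show any assessment taking place on the randomization date. The visit schedule belongs to the protocol. Section 6.1.2 says that demographics and baseline characteristics are recorded during screening, which Figure 3-1 allows to last up to 90 days. If the relevant readings were all made on earlier days, both arms use screening values and nothing differs. This stands: the effect is conditional on the schedule.

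Three further points also stand.

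- A reader might infer that vilaprisan dosing normally follows randomization by some days. The SAP shows only that a gap occurred in some subjects.
- A reader might assume that every ultrasound baseline is affected. For the largest fibroid, 6.2.3.3 places baseline before randomization in all groups, so a day-R scan is not baseline under that wording for vilaprisan either. It would still fall in TP1 in group B.
- A reader might put a hemoglobin figure on the bias. For two independent, equal-mean normal readings instead of one, the expected minimum falls by SD/√π = 0.564 SD. With an assumed within-subject SD of 0.5 to 1.0 g/dL this gives 0.564 × 0.5 = 0.28 to 0.564 × 1.0 = 0.56 g/dL. Neither the SD nor the step from one reading to two is in the SAP, and 6.5.3.6 also counts unscheduled measurements. From two readings to three the shift is only 0.846 − 0.564 = 0.282 SD. The documents do not support a size in g/dL.

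None of this removes the date conflict. The rule as written gives a day-R value a different status by arm, and no exception is stated.

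**Conclusion.** The point holds as a defect in a date boundary. Under Section 4.5 a visit-based value from the randomization date is always a TP1 value in group B, and is pre-treatment in any vilaprisan subject dosed on a later day. In the worst-value and any-occurrence summaries listed above, an untreated reading can then be reported as on-treatment in group B only.

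The size is unknown. It rests on two things that the SAP does not give: which assessments fall on the randomization date, and how many vilaprisan subjects started later. The documents do not support reading this as a threat to the primary safety comparison or to the secondary efficacy variable. Nor do they support saying that group B subjects have missing baselines, because no item is shown to be collected only on that date. The correction is worth making because it is specific, nearly free, and removes a difference between arms that comes from the date rule alone.

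**What to change.** In Section 4.5, add a rule for visit-based assessments:

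- In group B, baseline is the last non-missing value on or before the randomization date.
- In the vilaprisan groups, values from a scheduled pre-treatment assessment on the day of the first tablet count as baseline.
- Values assigned to baseline in this way are excluded from TP1.

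Then align the places that would otherwise conflict:

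- In 4.5, the end of the baseline phase and the exit-examination baseline.
- In 6.1.2, the wording about the reading nearest to study drug administration.
- In 6.2.3.3, the restriction of the largest-fibroid baseline to values before randomization.

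Leave the AE and diary intervals unchanged.

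The cost is a short rule, three aligned places, and a date comparison changed from < to ≤ for visit-based data. The small downside is that same-day values without a clock time are assumed to be pre-treatment.
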